We recently examined dietary intake of omega-3 fatty acids and AMD among 38,022 women in the Women's Health Study (WHS) who completed a dietary questionnaire at baseline and were free of a diagnosis of AMD. A total of 235 cases of visually significant AMD were confirmed during 10 y of follow-up. Women in the highest third of DHA intake had a 38% lower risk of AMD (RR, 0.62; 95% CI, 0.44-0.87) compared to those in the lowest third of intake. High intake of EPA was also associated with a reduced risk of AMD (RR, 0.66; 95% CI, 0.48-0.92). These prospective data from a large population of women appear to be the strongest evidence to date to support a role for DHA and EPA in the primary prevention of AMD.

Possible Mechanisms for Vitamin D in AMD - A plausible role for vitamin D3 in AMD prevention can be postulated due to its immunomodulatory, anti-inflammatory, and antiangiogenic properties. 1,25(OH)2D interferes with the activation and signaling of NF-κB.^{40, 41} 1,25(OH)2D decreases production of proinflammatory cytokines IL-2,42 IL-6,43 IL-8,44 and IL-12,45 increases production of the antiinflammatory cytokine IL-10,46 and regulates expression of matrix metalloproteinase-9.47 Vitamin D also lowers blood levels of C-reactive protein, a marker of systemic inflammation that we have prospectively linked to elevated risks of AMD in the WHS⁴⁸ and others have shown to be associated with AMD.⁴⁹⁻⁵² Vitamin D is a potent stimulator of mechanisms for pathogen elimination, which could be relevant given the possible involvement of chronic infection in AMD.53 In addition, vitamin D regulates the renin-angiotensin-aldosterone system (RAAS) via suppression of renin gene expression and biosynthesis,54 and could exert an indirect beneficial effect on AMD through improved blood pressure control. 55 Favorable effects of vitamin D on glucose tolerance and insulin sensitivity^{56, 57} could also mediate a beneficial effect in AMD as suggested by the association between dietary glycemic index and AMD. 58-62

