are consuming no more than 800 IU of vitamin D from all supplemental sources combined (individual vitamin D supplements, calcium+vitamin D supplements, medications with vitamin D [e.g., Fosamax Plus D], and multivitamins), or, if taking, willing to decrease or forego such use during the trial (to ensure the overall dose is well below the no-observed-adverse effect level (NOAEL) of 4000 IU specified by the European Commission Scientific Committee on Food (ECSCF); (8) are consuming no more than 1200 mg/d of calcium (the RDA) from all supplemental sources combined, or, if taking, willing to decrease or forego such use during the trial; (9) are not taking fish oil supplements, or, if taking, willing to forego their use during the trial; and (10) are willing to participate, as evidenced by signing the informed consent form.

IV. STUDY PROCEDURES

The procedures used to ascertain and document self-reports of AMD in *VITAL-AMD* are modeled on those used for more than two decades by the PIs in Physicians' Health Study I and II, Women's Health Study, and Women's Antioxidant Folic Acid Cardiovascular Study. All information is obtained masked to randomization status. Baseline and follow-up questionnaires are sent to study participants annually to obtain reports of diagnoses of AMD. Non-respondents are sent additional requests and are finally called to ensure complete follow-up. Reports of AMD may also be received through letters or telephone calls. Following the report of AMD, we obtain written consent to identify the diagnosing eye doctor(s) and obtain medical record information. We will contact the eye doctor(s) by mail and request they complete an AMD questionnaire or forward a complete copy of the patient's medical records pertaining to the diagnosis of AMD.

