AMD questionnaire - The AMD questionnaire asks about the date of initial diagnosis of AMD, the best-corrected visual acuity (VA) at the time of diagnosis, the date when VA reached 20/30 or worse, the most recent VA, and information about the pathological findings observed on exam (drusen, RPE hypo- &/or hyperpigmentation, geographic atrophy, RPE detachment, subretinal neovascular membrane, or disciform scar). The questionnaire will inquire about drusen size (small, intermediate, large) as well as information on the location of geographic atrophy (central versus noncentral). We will obtain information on treatments for AMD (laser, photodynamic, or anti-VEGF therapy). We will also obtain information about whether there are other ocular abnormalities that could explain or contribute to visual loss. If so, the eye doctor is asked to provide his/her judgment as to whether AMD, by itself, is significant enough to cause VA of 20/30 or worse. Once obtained, the medical record information will be evaluated by a single reviewer ([name]), masked to the treatment assignments, to determine conformity with uniform diagnostic criteria. In cases of uncertainty, [name] will also review the records. Reports for which doctors indicate diagnostic uncertainty will not be included as cases. When other ocular pathology is present, we will not include the case in our visually-significant AMD case group unless the examining eye doctor indicates their judgment that the AMD by itself would be sufficient to result in VA of 20/30 or worse. We define neovascular AMD by presence of RPE detachment, subretinal neovascular membrane, or disciform scar, either from clinical exam,

photos, or OCT if available, and will document the date of diagnosis of neovascular AMD.

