Assuming annual event rates for AMD observed in our previous trials of men and women, and an average follow-up of 6 years (expected for *VITAL*), *VITAL-AMD* will have good (≥80%) to excellent (≥95%) power to detect reductions of ≥20% in the primary AMD endpoint.

The study design is a 2x2 factorial randomized trial. With the large sample size, randomization should assure an equal distribution of known and unknown confounders between treatment groups, but we will control in analysis for any chance imbalances that may occur for AMD risk factors or conditions requiring more frequent medical attention that could increase the likelihood of AMD diagnosis. We will estimate the main treatment effects using the intention-to-treat principle based on randomized treatment assignment. Initial analyses of primary and secondary AMD endpoints will include contingency tables in which the rate of each endpoint (number of events per person-year of observation) among participants allocated to active treatment will be compared with the rate among those allocated to its placebo; controlling by stratification for the other treatment assignment. In addition, Kaplan-Meier survival estimates, the logrank test, and proportional hazards regression models201 will be used to determine whether there is a difference in time to an AMD event. Because an extended exposure to the study agents may be required to observe an effect, we will also conduct analyses which exclude AMD events that occur during the early years after randomization. To address the issue of AMD ascertainment, we will also test associations in models where the at-risk population during each 1 y follow-up period is restricted to those who report having had an eye exam during that year.

We will examine effect modification by the other randomized intervention, by race/skin pigmentation (for vitamin D), and by other risk factors by including an interaction term in proportional hazards models, as well as using methods for testing additive interactions. Stored blood samples will be used to measure genetic polymorphisms and analyses will examine the effect of these polymorphisms on the AMD endpoints, as well as modification of the treatment effects. These analyses will be analyzed as a nested case-control study using multivariable conditional logistic regression analyses and will also include testing of interactions on the additive scale.

VI. RISKS AND DISCOMFORTS

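### The exam-year sensitivity model counts AMD that arose in skipped years but drops those years, so it over-corrects if exam frequency among attenders differs by arm; an offset largely repairs this

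*Combined protocol and SAP*

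**What the plan says.** Section V makes intention-to-treat the main analysis, with rates expressed as "number of events per person-year of observation" and compared by randomized arm, followed by log-rank tests and proportional hazards models. It then adds a supporting analysis: "To address the issue of AMD ascertainment, we will also test associations in models" in which "the at-risk population during each 1 y follow-up period is restricted to those who report having had an eye exam during that year". The same section promises adjustment for chance imbalance in AMD risk factors or in "conditions requiring more frequent medical attention that could increase the likelihood of AMD diagnosis".

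Section IV fixes when an event happens. "The AMD questionnaire asks about the date of initial diagnosis of AMD", so a case enters the data when an eye doctor finds it, not when it starts. Planned follow-up is "an average follow-up of 6 years".

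Section V gives no term for time since the last exam, no rule for disease that began in an earlier unexamined year, and no interval-censored method. Neither section gives an expected exam uptake, overall or by arm.

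**The concern.** AMD does not go away between visits. A case that begins in a year without an exam waits and is found at the next one. The restricted risk set then contains the event but not the year in which the disease arose. The documents do not say outright that such cases are counted; it follows from putting the risk-set rule beside the dating rule.

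The rate per examined year is therefore roughly the onset rate times the average gap between exams. If one arm's attenders go less often, that arm shows more AMD per examined year even when onset is identical. The full analysis errs the other way, because the arm with fewer exams has fewer cases found by the end of follow-up.

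At stake is the plan's only check that uses eye-exam data. In one of the situations it is meant to address, it could suggest an effect that is not there or appear to contradict a sound main result.

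**Working it through.** **The plan's own figures.** There are none for exam uptake or for this analysis. The stated power (at least 80% to at least 95% for a 20% reduction) can be neither confirmed nor refuted, because the annual event rate is not printed. With two-sided 5% and 1:1 allocation (both assumed), hazard ratio 0.80 needs 631 events for 80% power and 1,044 for 95%. These counts serve only as a scale below.

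**Inputs.** From the documents: 6 years, yearly risk sets, events dated at diagnosis. Assumed: exam uptake, a rare and constant onset rate λ, everyone free of AMD at randomization, exams unrelated to symptoms.

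**Step 1: formula, independent yearly exams with probability p.** A case with onset in year j is found in year k with probability p(1−p)^(k−j). Summing over j = 1 to k, diagnoses per person in year k are λ[1−(1−p)^k].
- Full analysis: rate λ[1−(1−p)^k].
- Exam-year analysis: the same events over a fraction p of the person-time, so λ[1−(1−p)^k]/p.

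**Step 2: numbers.** Let m(p) be the mean of 1−(1−p)^k over k = 1 to 6. Then m(0.70) = 0.9286 and m(0.60) = 0.8893.
- Full ratio: 0.9286/0.8893 = 1.044.
- Exam-year ratio: 1.044 × 0.60/0.70 = 0.895.

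The year-stratified calculation gives 1.045 and 0.896. On the log scale the biases are 0.044 and −0.110.

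Onsets diagnosed in their own year number λp per person-year, so the share of counted events that arose in skipped years is 1 − p/m(p). At p = 0.70 this is 1 − 0.70/0.9286 = 0.25; it runs from about 0.40 at p = 0.50 to 0.17 at p = 0.80.

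**Step 3: when the new bias is the larger one.** No true effect throughout:

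| Assumed setting | Full | Exam-year |
|---|---|---|
| .80 v .70, independent, 6 y | 1.032 | 0.903 |
| .70 v .60, independent, 6 y | 1.045 | 0.896 |
| .50 v .40, independent, 6 y | 1.099 | 0.879 |
| .40 v .30, independent, 6 y | 1.161 | 0.871 |
| .70 v .60, independent, 3 y | 1.088 | 0.932 |
| .70 v .60, within-person correlation 0.5, 6 y | 1.10 | 0.945 |
| .70 v .60, within-person correlation 0.8, 6 y | 1.137 | 0.974 |
| .70 v .60, fixed always/never attenders, 6 y | 1.168 | 1.000 |

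In the first three rows the exam-year bias is larger on the log scale. In the rest it is smaller. The crossover is near 35% to 40% uptake with independent exams, and at a within-person correlation of roughly 0.25 to 0.45, depending on uptake. The 0.945 depends slightly on how the correlation is modelled; another form gives 0.941.

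**Step 4: cases with no bias.** Equal uptake (.70 in both arms) gives 1.000 in both analyses. Attenders examined at 60% a year in both arms, with 40% v 45% never examined, give 1.10 full and 1.00 exam-year. Here the restriction does its job.

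**Step 5: the alternative.** A model at each reported exam, with an offset for log years since the previous one, gave 0.99 to 1.01 under the null for uptake .60 v .55, .70 v .60 and .70 v .50 and correlations from 0 to 0.8. It gave 0.80 to 0.81 when the true hazard ratio was 0.80. For comparison, at .70 v .60 with independent exams and a true 0.80, the full analysis gives 0.836 and the exam-year analysis 0.717.

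**The case against.** The strongest reply is that uptake has little reason to differ. The trial is randomized, and "All information is obtained masked to randomization status". With about 10,000 per arm (1:1 assumed) and 60% uptake, the standard error of a one-year difference is √(2 × 0.6 × 0.4/10,000) = 0.007, so a 10-point gap is about 14 standard errors. A chance gap of 2 standard errors (.60 v .586) gives about 1.01 full and 0.985 exam-year, and a type I error of about 5.7% at 1,044 events. This stands. A material bias needs an agent that changes how often people see an eye doctor.

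A reader might infer that the plan itself predicts such a change, since Section I cites "Favorable effects of vitamin D on glucose tolerance and insulin sensitivity". It does not. That passage concerns a biological route to AMD and says nothing about eye-care attendance, and the Section V remark on medical attention concerns chance imbalance to be adjusted for. A link to exam frequency is conjecture.

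A reader might also infer that the restriction always replaces one bias with a larger one, or that it works only if every attender goes yearly. The table and Step 4 rule out both: persistent habits, low uptake or short follow-up make the new bias the smaller one, and equal frequency among attenders is enough to remove it.

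Nor is this the plan's only protection against uneven detection. There is the covariate adjustment, and Section IV has a pilot in 500 participants to estimate sensitivity of case detection. Neither uses exam timing during follow-up.

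Finally, the offset model has a weakness of its own. If symptoms prompt exams, it is biased too: about 0.94 at .70 v .60 under the null, against about 0.87 for the exam-year model. In such settings the full analysis can be closest to 1 (1.022 at .70 v .50 in one simulation, where the offset model gave 0.923).

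**Conclusion.** The point holds as a cheap improvement to a supporting analysis, not as an error that threatens the trial's result. The risk-set rule and the dating rule together keep events while discarding the time in which some of them arose. Where exam frequency among attenders differs by arm, the exam-year ratio is pushed in the opposite direction to the full analysis. At an assumed 70% v 60%, 6 years and no true effect, it is 0.896 with independent exams and 0.945 at within-person correlation 0.5. It exceeds the bias it is meant to remove only when attendance is irregular from year to year, uptake is above roughly 40% and follow-up is about 6 years; otherwise it is smaller, though present until attendance becomes fixed.

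All sizes rest on uptake, correlation and exam-timing assumptions that the documents do not supply. Uptake gaps this large are unlikely here, and the main intention-to-treat analysis is not affected.

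**What to change.** In Section V, replace or supplement the restriction with this analysis. At each reported exam, model diagnosis of AMD with a complementary log-log (grouped proportional hazards) model by randomized arm, with offset log(years since the previous reported exam, or since randomization for the first), censoring at the last reported exam. An interval-censored proportional hazards model running from the last AMD-free exam to the diagnosing exam would serve equally. Report exam uptake by arm and year, so that readers can see whether the question arises at all.

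The cost is a sentence or two, one offset term and a small table. The yearly exam reports are already needed for the planned model. State the assumption that exam timing is not driven by symptoms, and present the result beside the intention-to-treat estimate rather than in place of it.

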- 6. Are there associations of polymorphisms in CYP24A1, vitamin D receptor, desaturase genes, or other genes with functional relevance to vitamin D and omega-3 fatty acid pathways with incidence of AMD?
- 7. Do polymorphisms in CYP24A1, the vitamin D receptor, complement factor H, ARMS2, C3, C2/BF, RORA, or other functionally relevant genes modify the effects of vitamin D3 on the AMD endpoints?
- 8. Do polymorphisms in desaturase genes (FADS1, FADS2, FADS3), elongase of very long fatty acids 2 (ELOVL2), complement factor H, ARMS2, C3, C2/BF, RORA, or other functionally relevant genes modify the effects of EPA+DHA on the AMD endpoints?

Secondary aims 6, 7, and 8 will be addressed in the subgroup which provides a baseline blood specimen using a nested case-control sample of all AMD cases (incident AMD cases and progression to advanced AMD) and a set of age- and sexmatched controls remaining free of AMD.

III. SUBJECT SELECTION/ENROLLMENT

VITAL-AMD is an ancillary study of the NIH-funded **VITAL** trial. All persons randomized in **VITAL** are included in this ancillary study.

Individuals are eligible for *VITAL* trial participation if they meet the following criteria: (1) are age ≥60 (men) or ≥65 (women); (2) have at least a high school education (to complete mail-based questionnaires); (3) have no history of cancer (except non-melanoma skin cancer), MI, stroke, TIA, angina pectoris, CABG, or PCI; (4) have none of the following safety exclusions: history of kidney stones, renal failure or dialysis, hypercalcemia, hypo-or hyperparathyroidism, severe liver disease (cirrhosis), or sarcoidosis or other granulomatous diseases such as active chronic tuberculosis or Wegener's granulomatosis; (5) have no allergy to fish (for EPA+DHA); (6) have no other serious illness that would preclude participation; (7)

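### For incident AMD, the planned matched analysis of gene-by-supplement interaction (aims 7 and 8) is valid but does not use the genotype-treatment independence that randomization provides, and so loses precision

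*Combined protocol and SAP*

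**What the plan says.** Section II sends secondary aims 6, 7 and 8 to the baseline-blood subgroup, "using a nested case-control sample of all AMD cases (incident AMD cases and progression to advanced AMD) and a set of age- and sexmatched controls". It gives no number of controls per case. Aim 6 concerns genotype associations with AMD. Aim 7 asks whether named genes "or other functionally relevant genes modify the effects of vitamin D3 on the AMD endpoints", and aim 8 whether they "or other functionally relevant genes modify the effects of EPA+DHA on the AMD endpoints".

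Section V covers both kinds of question together: "analyses will examine the effect of these polymorphisms on the AMD endpoints, as well as modification of the treatment effects". The next sentence names the method, "These analyses will be analyzed as a nested case-control study using multivariable conditional logistic regression analyses", and adds that the work "will also include testing of interactions on the additive scale". Interaction terms in proportional hazards models are planned for the other agent, for race or skin pigmentation and for other risk factors. The genetic analyses are assigned to the case-control sample. Randomization is mentioned only as a source of confounder balance. Neither a case-only analysis nor an estimator that imposes gene-treatment independence is named, and no power is given for aims 7 and 8.

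**The concern.** Germline genotype is settled before randomization, and the specimen is a baseline one. Among blood donors, genotype and assigned treatment are therefore independent by design. The same is true among donors free of AMD at baseline, because that restriction also precedes randomization.

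A matched conditional logistic model with a genotype-by-treatment term in effect compares the genotype-treatment odds ratio in cases with that in controls. The control odds ratio is already known to be about 1, so estimating it only adds sampling error. Regressing treatment on genotype among cases alone targets the same multiplicative interaction without that error. The usual objection to case-only analysis, that gene and exposure may be correlated in the population, does not arise when the exposure is randomized.

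What is at stake is precision. The number of AMD cases is fixed by incidence, and the two aims name seven and nine genes or gene regions, with others left open. Confidence intervals for gene-by-treatment interaction on incident AMD would be wider than these data require.

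**Working it through.** **Plan's own figure.** There is none for aims 7 and 8. The only power statement (section V) concerns reductions of 20% or more in the primary endpoint. It cannot be reproduced, because the annual rate and alpha are not given. At an assumed two-sided 5%, a hazard ratio of 0.8 with 80% power needs 4 × (1.960 + 0.842)² / (ln 0.8)² = 631 events. If 80% of cases gave blood (16,000 of 20,000), that is about 505 genotyped cases, so 500 is a reasonable working number.

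**Assumptions, none stated in the documents.** 500 genotyped incident cases; 40% carriers; equal allocation; no main effect of genotype or treatment; interaction ratio 1 or 0.6; m = 1, 2 or 4 controls per case; AMD uncommon enough that controls reflect the donors.

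**Formulas.** The variance of the log interaction is
- case-only: V₀ = sum of 1/n over the four genotype-by-treatment case cells;
- case-control: V₀ + V_c/m, where V_c is the same sum over the control cells at 1:1. This is the unconditional form; the exact conditional-logistic information for 1:m sets gives the same shares when there are no effects.

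**No interaction.** Case cells are 150, 150, 100 and 100, so V₀ = 2/150 + 2/100 = 0.0333, and V_c is the same. The planned method keeps V₀/(V₀ + V_c/m) = m/(m + 1) of the case-only information: 50%, 67% and 80% at 1:1, 1:2 and 1:4. The loss is 50%, 33% and 20%.

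**Interaction ratio 0.6.** Case cells become 163.0, 163.0, 108.7 and 65.2, so V₀ = 0.0368, and V_c = 0.0333. Power = Φ(0.511/SE − 1.96), where 0.511 = |ln 0.6|.

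| Analysis | Variance | SE | Case-only variance as share | Power |
|---|---|---|---|---|
| Case-only | 0.0368 | 0.192 | 100% | 76% |
| 1:1 | 0.0701 | 0.265 | 52% | 49% |
| 1:2 | 0.0535 | 0.231 | 69% | 60% |
| 1:4 | 0.0451 | 0.212 | 82% | 67% |

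**Uncommon variant, strong effect.** Take 10% carriers, genotype risk ratio 5, treatment ratio 0.8 and interaction 0.7. The case cells are 187.5, 150, 104.2 and 58.3, and the 1:1 control cells are 225, 225, 25 and 25. Then V₀ = 0.0387 and V_c = 0.0889, and the share kept at 1:1 is 0.0387/0.1276 = 30%. The exact conditional calculation gives 28%. The share can also be slightly above half: 56% with 50% carriers and the same effects.

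**Check by simulation (505 cases, 30% carriers, 1:1, 1,500 replicates).** With no effects, the SD was 0.280 for conditional logistic and 0.202 for case-only, a share of 0.52. With genotype ratio 2.5, treatment ratio 0.8 and interaction 0.7, the mean log interaction was −0.366 and −0.363, against a true −0.357. Both methods centre on the truth.

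**The case against.** The strongest reply is that nothing is wrong with the plan. Matched conditional logistic regression is a valid interaction test. In separate simulations of the whole design with no interaction, it rejected 4.0% (400 replicates) and 5.5% (1,500 replicates) of the time. These are secondary aims, and the controls must be genotyped anyway for aim 6 and the additive tests, so one framework for all three is defensible. This stands: the point is about efficiency, not error.

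Four stronger readings are tempting, and the documents do not support them.

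- *Half the information is lost.* That is the 1:1 figure with small effects. Section II does not give the matching ratio, and at 1:4 the loss is about 20%. Nor is half a ceiling, as the uncommon-variant case shows. The loss also concerns one interaction parameter, not everything the cases tell us.
- *Conditional logistic regression is the only interaction test planned.* The same sentence adds additive-scale tests, which case-only data cannot supply.
- *The case-only test should replace the planned one throughout.* The sampled cases include progression to advanced AMD. Among people whose AMD arose after randomization, the group at risk of progressing is selected on an event that genotype and treatment may both have affected. Independence is then not guaranteed. It does hold among those with AMD at baseline.
- *The planned method is why real modification would be missed.* The two aims name 7 + 9 = 16 gene-agent pairs. At 0.05/16 (critical value 2.955), with the other inputs unchanged, power is 39% case-only against 15%, 23% and 29% at 1:1, 1:2 and 1:4. The relative gain remains, but neither method is then well powered.

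**Conclusion.** The point holds as a cheap gain in precision for the multiplicative interaction on incident AMD. The loss under the planned model is about 50%, 33% or 20% of the information at 1:1, 1:2 or 1:4 with small effects. It is larger for uncommon variants with strong effects.

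Two facts from the documents carry the conclusion: treatment is randomized, and genotype comes from a baseline specimen. It also takes blood donation to be unaffected by assignment. The power figures are illustrations only: case count, carrier share, interaction ratio, alpha, allocation ratio and matching ratio are all assumed. A reader might infer that the planned results would be biased or that the controls are unnecessary; neither follows.

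**What to change.** For aims 7 and 8 and incident AMD, pre-specify as the main multiplicative interaction test a logistic regression of randomized assignment on genotype among genotyped cases, with the randomization ratio as an offset and the other agent as a covariate. A case-control likelihood that imposes gene-treatment independence would serve equally. Keep the matched conditional logistic model for aim 6 and the case-control data for the additive-scale interactions. For progression to advanced AMD, use the case-only test only among participants with AMD already present at baseline, and keep the planned model where AMD arose after randomization. State the number of controls per case.

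The cost is analysis-plan wording, with no new samples or genotyping. The small downside is that case-only data give the multiplicative scale only, approximating a risk-ratio interaction, so the controls are still needed. Naming the main test in advance also avoids a choice between estimators after the results are seen.
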